1.0 Background

Diabetes is a major global health concern, associated with significantly increased mortality and high incidence of co-morbidities¹. Given the high rate of cardiovascular and other diseases in individuals with diabetes, diabetes-related mortality may be underestimated and is estimated to be the third largest cause of death in the US². Treatment efficacy and successful disease management varies between patients. This is in part attributable to the fact that diabetes is a heterogeneous disease, with multiple underlying causes. In a small proportion of cases of monogenic diabetes, the defects have been identified by genetic testing, sometimes leading to vastly improved treatment strategies^{3,4}. However, the vast majority of cases of diabetes are polygenic and multifactorial. Despite some understanding of disease pathophysiology, and a variety of treatment options, the underlying causes of diabetes are unknown in most cases. A broader understanding of the variety of paths that lead to diabetes could identify alternative therapeutic targets. This may be crucial to preventing or managing disease in specific subsets of patients. Large-scale metabolomics studies have successfully identified novel candidates for diabetes, including a novel diabetes biomarker, aaminoadipic acid (2-AAA, **Figure 1**), which predicts the development of diabetes in humans⁵. In matched diabetes cases and controls from the Framingham Heart Study (FHS), higher plasma 2-AAA (at baseline) was associated with future diabetes, independent of fasting glucose and other known risk markers (age, sex, BMI, family history, diet)5.

Source of 2-AAA: 2-AAA is generated from the catabolism of the amino acid lysine through the saccharopine (mitochondrial) and/or the pipecolic acid (peroxisomal) pathways^{6,7} (Figure 2). Both pathways converge in the generation of 2-aminoadipate-6-semialdehyde, which is then further metabolized to 2-AAA in the cytosol⁸. 2-AAA is subsequently metabolized to 2-oxoadipate (a-ketoadipic acid), and further to acetyl-coA, entering the TCA cycle. Lysine is an essential amino acid which is acquired from dietary sources, with a recommended daily intake of 30mg/kg/day⁹. A portion of lysine in humans may be derived from the microbiome, with bacteria and fungi capable of de novo synthesis, in addition to modulation of bioavailability of dietary sources¹⁰.

Genetics: Variation in genes encoding enzymes in the lysine degradation pathway (indicated in boxes in **Figure 2**) may influence 2-AAA levels and downstream function. The strongest

Figure 1. L-α-aminoadipic acid Mitochondrion Lysine 2-Oxoglutarate AASS Peroxisome : Saccharopine Pipecolate **J**PIPOX AASS . 1-Piperideine-2-Aminoadipate-6-carboxylate 6-semialdehyde AASDH, ALDH7A1 2-Aminoadipic acid AADAT DHTKD1 Glutaryl-CoA 2-Oxoadipate **GCDH** Crotonyl-CoA Acetyl-CoA Cytosol TCA Cycle

Figure 2. Multicompartmental model of L-lysine degradation (Adapted from Danhauser et al. 2012)

evidence thus far exists for *DHTKD1*, variation in which has been associated with 2-Ketoadipic, 2-Aminoadipic and 2-Oxoadipic Aciduria^{8,11}, and Charcot-Marie-Tooth

Disease¹². *DHTKD1* expression correlates with ATP production in mitochondria *in vitro*, and siRNA knockdown of *DHTKD1* leads to impaired mitochondrial biogenesis and increased reactive oxygen species production, resulting in apoptosis and reduced cell growth¹³. Variation in mouse *Dhtkd1* has been found to associate with expression of the gene (eQTL) and levels of protein (pQTL) in liver, as well as with serum 2-AAA levels¹⁴. Liver *Dhtkd1* expression correlated significantly with serum 2-AAA in these mice. Further, liver 2-AAA was negatively associated with liver mass, fasting glucose and serum cholesterol while higher liver 2-AAA was associated with higher insulin sensitivity.

2.0 Rationale and Specific Aims

Diabetes is a significant contributor to mortality and morbidity. The lysine-derived metabolite a-aminoadipic acid (2-AAA) has been identified as a novel predictor of diabetes development in humans, potentially identifying at-risk individuals before development of other known risk markers. Little is known about the function of 2-AAA.Our preliminary investigation of human clinical, human genetic, animal and cell experimental data has revealed multiple lines of evidence supporting 2-AAA and its pathway as biologically relevant to diabetes pathophysiology. However, it is not yet clear whether 2-AAA is itself causal in diabetes development, or is a biomarker for altered metabolic processes, and many questions remain as to mechanisms of action. The determinants of variation in 2-AAA levels between individuals are not known. The aim of the first phase of this study (2-AAA Screening study, ongoing) was to measure plasma 2-AAA levels from healthy individuals from the general population, to identify subjects with extremely high or low 2-AAA (defined as top and bottom 10%-25% of distribution). In this second phase of the study, individuals with high or low 2-AAA will be invited to participate in a dietary lysine modification study, to assess the effect of controlled lysine intake on plasma and urine 2-AAA.

Specific Aim: Determine whether plasma 2-AAA levels are responsive to dietary intervention within individuals in the extremes of 2-AAA distribution in the general population. We hypothesize that plasma 2-AAA levels in a well-nourished population are determined by genetics and gene-diet interactions and are not simply a reflection of dietary lysine exposure. Based on plasma 2-AAA measurements in our Phase 1 Screening study (ongoing, planned N=400), we will invite subjects who fall in the top and bottom ~10% of circulating 2-AAA (up to N=80) to return for future study. We will implement a dietary intervention to assess whether 2-AAA is a biomarker of lysine intake, or if 2-AAA levels are determined by genetic or gene-diet effects. Subjects will consume two different diets ("normal" and "high" lysine) in a randomized order (one week each), separated by a 2-week habitual diet washout period.

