Observational data in humans does not support a relationship between dietary intake of protein or lysine and 2-AAA (as assessed in FHS⁵, and our own preliminary data). There are limited data on 2-AAA in response to dietary intervention. There was no change in 2-AAA in obese subjects following 16 weeks of caloric restriction, despite weight loss²⁸. However, dietary protein was not altered in this study. In a multi-diet comparison, 2-AAA decreased on a low fat diet, and increased on a very-low carbohydrate diet²⁹. The relationship between dietary lysine and 2-AAA has never been assessed through a randomized intervention trial. We will address this in the current study. One week of diet is appropriate to identify short-medium term dietary biomarkers³⁰, but not long enough to affect other variables (which could alter 2-AAA through reverse causation).

We have already analyzed plasma samples for the first 122 participants of phase 1 of the study. As expected, there was variability in plasma 2-AAA, with some evidence for

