4.0 Inclusion/Exclusion Criteria

Inclusion Criteria:

- Prior participant in 2-AAA screening study.
- Identified as eligible due to high or low plasma 2-AAA, in the absence of hyperglycemia, as defined by study team.

Exclusion Criteria:

- Individuals who currently use tobacco products.
- Use of prescription or over-the-counter medications or dietary supplements which could modulate levels of 2-AAA and unwilling to discontinue use (from 24 hours prior to first study visit until completion of study). Hormonal birth control is acceptable.
- Follow a severely restricted diet or have food allergies, which would preclude adherence to study diet.
- Newly diagnosed disease (since screening visit), including cardiovascular, renal, or liver disease, or Diabetes mellitus.
- Individuals who are pregnant or lactating
- · Inability to provide written or electronic informed consent
- Inability to fast for 8 hours

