5.0 Enrollment/Randomization

We will enroll up to 80 subjects who meet the inclusion and exclusion criteria. We will identify potential participants based on their results from the screening study. We will contact eligible participants directly, by email or phone, and invite them to participate.

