6.0 Study Procedures

The study will be conducted as a randomized crossover dietary intervention, with 4 separate study visits (Figure 4). Individuals will be randomized to normal or high lysine diet for 1 week, followed by a 2-week washout, where participants return to their habitual diet. They will then complete the second 1-week dietary intervention. The entire study period encompasses 4 weeks.

[figure not shown]

Figure 4. Overview of the proposed dietary intervention study.

Screening

Subjects will be screened based on their 2-AAA levels and other data obtained during phase 1 of the study. Inclusion/exclusion criteria will be reviewed to confirm that the subject meets study eligibility requirements. Individuals who meet the inclusion criteria, and do not meet any of the exclusion criteria will be invited to participate in the study. Informed consent will be obtained via telephone with a phone consent witness or electronically. All participants will be instructed to discontinue use of over-the-counter medications and supplements on the day prior to the study visit. Participants will be asked about any major changes to their diet since their screening visit, and if any changes are reported, they will be asked to complete an online food frequency questionnaire (DHQ III) at any time before their visit (Food Frequency Questionnaire Instructions, **Appendix A**). In addition, participants will be asked to complete a 24-hour diet recall (ASA24) around the time of each study visit (Diet Recall Instructions, **Appendix A**). As part of the screening questionnaire, participants will be asked about their physical activity to ascertain their energy requirements for the dietary intervention. Participants will be asked to pick up a stool collection kit from the study coordinator (from the Preston Research Building, or another convenient location) prior to their first visit. If you are a woman and are able to become pregnant, you will have a urine pregnancy test to make sure that you are not pregnant before you receive treatment in this study.

Study Visits

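### Do the two percentile ranges for high and low 2-AAA in section 2.0 leave the study population undefined?

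*Combined protocol and SAP*

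**What the plan says.** Section 2.0 contains two percentile statements. The account of phase 1 describes extremely high or low 2-AAA as "defined as top and bottom 10%-25% of distribution", and the next sentence says that "individuals with high or low 2-AAA will be invited to participate in a dietary lysine modification study". The Specific Aim, which concerns the diet study itself, says "we will invite subjects who fall in the top and bottom ~10% of circulating 2-AAA (up to N=80) to return for future study". It ties this to the "Phase 1 Screening study (ongoing, planned N=400").

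The operative inclusion criterion in section 4.0 gives neither a percentile nor a concentration: "Identified as eligible due to high or low plasma 2-AAA, in the absence of hyperglycemia, as defined by study team". Section 5.0 selects from the screening results without a cut-off and sets the size: "We will enroll up to 80 subjects who meet the inclusion and exclusion criteria". Section 10.0 splits that ceiling into 40 high and 40 low. Section 3.0 reports progress in phase 1: "We have already analyzed plasma samples for the first 122 participants of phase 1 of the study".

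**The concern.** The Specific Aim is about people at the extremes of the 2-AAA distribution, so the cut-off defines who is studied. A reader finds one statement that allows anything from 10% to 25% per tail, another at about 10%, and an eligibility criterion that names neither. Because the sentence after the wider range carries high and low 2-AAA into the diet study, the wider range could be thought to apply there too.

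Three things would then be at stake. First, the pool could differ by as many as 120 people. Second, with 10% tails the pool equals the ceiling, so any refusal or exclusion leaves smaller groups or requires wider tails. Third, screening was still under way, and the available text does not say whether percentiles are taken from the values so far or from all 400. A reader might be unable to tell how extreme the groups were, or to repeat the selection.

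**Working it through.** **Inputs.** Planned phase 1 size 400, cut-offs ~10% and 10% to 25% (section 2.0); first 122 analysed (section 3.0); ceiling 80 = 40 + 40, 39 subjects for the diet effect, and 1.6-fold diabetes risk per SD of 2-AAA (section 10.0).

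**1. The plan's own figure.** Pool = 2 x cut-off x 400. At 10%: 2 x 0.10 x 400 = 80, or 40 per tail. This equals the stated 80 and the stated 40 + 40.

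**2. The pool across the wider range.**

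| Cut-off per tail | Pool | More than at 10% | Share of pool needed to reach 80 |
|---|---|---|---|
| 10% | 80 | 0 | 100% |
| 15% | 120 | 40 | 67% |
| 20% | 160 | 80 | 50% |
| 25% | 200 | 120 | 40% |

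The difference between the statements therefore runs from 0 to 120 people. The upper end is 2 x (0.25 - 0.10) x 400 = 120, which is 30% of 400, and it arises only if the range is read at 25%.

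**3. How extreme the groups would be.** Assume 2-AAA, or a transform of it, is normal. The mean of a tail holding a share c is then pdf(z)/c.
- At 10%: z = 1.282, tail mean 1.755 SD, high-low separation 2 x 1.755 = 3.51 SD.
- At 25%: z = 0.674, tail mean 1.271 SD, separation 2.54 SD.

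At 1.6-fold per SD, the implied risk ratio between groups is 1.6^3.51 = 5.2 or 1.6^2.54 = 3.3. The groups are far apart under either reading.

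**4. Percentiles from 122 or from 400.** With no distribution assumed, the population share above the 12th highest of 122 values follows Beta(12, 111), with a 95% range of 5.2% to 15.6%. For the 40th highest of 400 it follows Beta(40, 361), with a range of 7.2% to 13.1%. A sample 10% cut-off is only approximate even when all 400 are used. The wider range matters only if invitations begin early, which the documents do not state.

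**5. Numbers for the diet effect.** Taking 39 as a total, 39/80 = 49% of the pool at 10% and 39/200 = 20% at 25%. If 39 were meant per group, 2 x 39 = 78 would be needed: 78/80 = 98% at 10%, and 78/200 = 39% at 25%.

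**The case for a change.** The strongest case is that the ~10% reading leaves no slack. Section 4.0 excludes tobacco users, people who will not stop certain medications or supplements, those on severely restricted diets, those with newly diagnosed disease, and those who are pregnant or lactating. Hyperglycemia also disqualifies. Filling 40 + 40 from a pool of 80 would need every one of them to be eligible and to accept. Some widening is therefore likely, and no written rule governs it. If 39 is a per-group requirement, a shortfall would also reduce power within a group.

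Part of this stands. The text does not say outright that ~10% governs, and a rule for widening would make the selection easier to repeat. The rest is weaker. Sections 2.0, 5.0 and 10.0 all give 80 as an upper limit, so smaller groups are permitted. The cut-off is stated as approximate, and the same section names 25% as the outer edge of what counts as extreme, so the direction and limit of any widening can be read from the text. Section 10.0 states no within-group test, and whether 39 is a total or per group is a separate question that the cut-off does not settle.

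The point about the reference distribution cannot be pressed. The Specific Aim links the percentile to the study planned at 400, and the available text of section 3.0 breaks off where the 122 values are being described. A rule based on all values available at each invitation date would not clearly help: the threshold would move, so the same 2-AAA value could qualify on one date and not on another.

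**Conclusion.** The concern is accurate about the wording but does not call for a change. The two statements serve different purposes: the 10% to 25% range describes what phase 1 set out to find, and ~10% is the only percentile attached to inviting people to the diet study. The second lies inside the first and reproduces the planned 80 exactly. The ambiguity is 0 to 120 of 400 people, with 120 as the extreme reading.

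The primary comparison is a randomized crossover within person, so following the plan as written gives a sound estimate of the diet effect whichever percentile formed the groups. The cut-off affects how far apart the groups are (3.51 against 2.54 SD, if 2-AAA is normal) and so how the high-low contrast is described. A study team would sensibly start at about 10%, widen within the stated range if needed, and report where participants fell in the final phase 1 distribution. This is a gap in detail that ordinary practice fills. The conclusion assumes that the study team's definition in section 4.0 stays within the 10% to 25% range of section 2.0.

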3.0 Animal Studies and Previous Human Studies

[figure not shown]
2-AAA has been identified as a marker of oxidative stress in C. *elegans*, and in endothelial cells in response to hyperglycemia¹⁵, highlighting a potential mitochondrial phenotype, and relationship between 2-AAA and reactive oxygen species (ROS)^{16,17}. In

animal models, administration of 2-AAA resulted in increased insulin levels and lower fasting plasma glucose, but no change in peripheral insulin sensitivity as measured by insulin tolerance test⁵. *In vitro* 2-AAA treatment has been shown to enhance insulin secretion in pancreatic β cells and islets. 2-AAA is thought to have important functions in the brain¹⁸, as well as in other organs, including liver and pancreas.

High baseline plasma 2-AAA in healthy individuals was associated with increased future risk of diabetes (12-year follow-up) in FHS participants and validation samples (N~2,000)⁵. Insulin sensitizing therapy leads to reduction in 2-AAA, but not other putative diabetes-biomarkers, including branched-chain amino acids (BCAAs)¹⁹. Increased 2-AAA is found in skin in the setting of diabetes, as well as in chronic renal failure and sepsis, and increases with age²⁰. Further, decreased urine 2-AAA has been reported in diabetes patients compared with non-diabetic¹⁴, highlighting a likely complex feedback relationship between 2-AAA levels and early diabetes development vs. the setting of established disease. Treatment of overweight/obese adults with impaired fasting glucose or untreated diabetes with pioglitazone (45 mg/day) and metformin (1000 mg twice/day) led to a significant reduction in plasma 2-AAA and lysine, concurrent with an increase in insulin sensitivity¹⁹. Acute insulin infusion (7 hrs) in these subjects also led to a decrease in both lysine and 2-AAA^{19,21}. The epilepsy drug vigabatrin, which acts through GABA transaminase inhibition, leads to increased 2-AAA in plasma and urine, to levels similar to those seen in alpha-aminoadipic aciduria²². Apart from diabetes, 2-AAA has been found to be elevated in the setting of other cardiometabolic or inflammatory diseases including atherosclerosis²³, chronic renal failure and sepsis²⁰, non-alcoholic fatty liver disease (NAFLD)²⁴ and polycystic ovary syndrome (PCOS)²⁵. There is likely some reciprocal regulation between insulin and 2-AAA: insulin infusion in humans leads to decreased 2-AAA^{19,21,26}, while insulin deprivation and hyperglycemia in the setting of type 1 diabetes leads to increased 2-AAA²⁷.

Observational data in humans does not support a relationship between dietary intake of protein or lysine and 2-AAA (as assessed in FHS⁵, and our own preliminary data). There are limited data on 2-AAA in response to dietary intervention. There was no change in 2-AAA in obese subjects following 16 weeks of caloric restriction, despite weight loss²⁸. However, dietary protein was not altered in this study. In a multi-diet comparison, 2-AAA decreased on a low fat diet, and increased on a very-low carbohydrate diet²⁹. The relationship between dietary lysine and 2-AAA has never been assessed through a randomized intervention trial. We will address this in the current study. One week of diet is appropriate to identify short-medium term dietary biomarkers³⁰, but not long enough to affect other variables (which could alter 2-AAA through reverse causation).

We have already analyzed plasma samples for the first 122 participants of phase 1 of the study. As expected, there was variability in plasma 2-AAA, with some evidence for

4.0 Inclusion/Exclusion Criteria

Inclusion Criteria:

- Prior participant in 2-AAA screening study.
- Identified as eligible due to high or low plasma 2-AAA, in the absence of hyperglycemia, as defined by study team.

Exclusion Criteria:

- Individuals who currently use tobacco products.
- Use of prescription or over-the-counter medications or dietary supplements which could modulate levels of 2-AAA and unwilling to discontinue use (from 24 hours prior to first study visit until completion of study). Hormonal birth control is acceptable.
- Follow a severely restricted diet or have food allergies, which would preclude adherence to study diet.
- Newly diagnosed disease (since screening visit), including cardiovascular, renal, or liver disease, or Diabetes mellitus.
- Individuals who are pregnant or lactating
- · Inability to provide written or electronic informed consent
- Inability to fast for 8 hours

5.0 Enrollment/Randomization

We will enroll up to 80 subjects who meet the inclusion and exclusion criteria. We will identify potential participants based on their results from the screening study. We will contact eligible participants directly, by email or phone, and invite them to participate.

6.0 Study Procedures

The study will be conducted as a randomized crossover dietary intervention, with 4 separate study visits (Figure 4). Individuals will be randomized to normal or high lysine diet for 1 week, followed by a 2-week washout, where participants return to their habitual diet. They will then complete the second 1-week dietary intervention. The entire study period encompasses 4 weeks.

[figure not shown]

Figure 4. Overview of the proposed dietary intervention study.

Screening

Subjects will be screened based on their 2-AAA levels and other data obtained during phase 1 of the study. Inclusion/exclusion criteria will be reviewed to confirm that the subject meets study eligibility requirements. Individuals who meet the inclusion criteria, and do not meet any of the exclusion criteria will be invited to participate in the study. Informed consent will be obtained via telephone with a phone consent witness or electronically. All participants will be instructed to discontinue use of over-the-counter medications and supplements on the day prior to the study visit. Participants will be asked about any major changes to their diet since their screening visit, and if any changes are reported, they will be asked to complete an online food frequency questionnaire (DHQ III) at any time before their visit (Food Frequency Questionnaire Instructions, **Appendix A**). In addition, participants will be asked to complete a 24-hour diet recall (ASA24) around the time of each study visit (Diet Recall Instructions, **Appendix A**). As part of the screening questionnaire, participants will be asked about their physical activity to ascertain their energy requirements for the dietary intervention. Participants will be asked to pick up a stool collection kit from the study coordinator (from the Preston Research Building, or another convenient location) prior to their first visit. If you are a woman and are able to become pregnant, you will have a urine pregnancy test to make sure that you are not pregnant before you receive treatment in this study.

Study Visits

There will be four separate study visits. All study visits will follow similar procedures. Subjects will be requested to arrive at a research room in the Preston Cancer Research building or the Vanderbilt Clinical Research Center on the morning of each study visit (~7:00 - 11:00 AM) in a fasting state (at least 8 hours, with no food or drink, excluding water). At the first visit, after informed consent has been reviewed and documented, inclusion/exclusion criteria will be reviewed to confirm that the subject meets study eligibility requirements. Subject's medical history and medications will be discussed and documented by study personnel to assess for any changes that may potentially exclude the subject from participating. Study personnel will collect the subject's blood pressure, heart rate, height, weight, waist and hip circumference. All subjects will be asked to provide a urine sample. Subjects will be asked to provide a drop of blood via fingerprick for measurement of fasting glucose. Venipuncture will be performed to obtain a blood sample (~50ml). All subjects will be asked to bring a stool sample (collected in the 24 hours prior to each study visit) and will be given additional collection kits for subsequent samples at their study visits. Participants will be asked to fill out a questionnaire to assess general wellbeing and mental health (PHQ).

Diet

Subjects will meet with a dietician and be provided a menu, shopping list, and a gift card to purchase foods to prepare 3 meals and 1-2 snacks per day during the study period. All subjects will consume the same foods for both dietary periods (normal lysine and high lysine, 1 week each), with lysine supplements (5g/day) included for the high lysine diet period. Menus will be developed by the study dietitian ([name], Co-I). Energy content of meals will be personalized for each participant based on the individual's estimated daily energy requirement using the Harris Benedict Equation with an activity factor of 1.2.

Compensation

Subjects will receive \$250 following successful completion of the study visit.

Biomarkers

Blood, urine and stool samples will be coded for subject confidentiality. Plasma, serum, buffy coat, stool and urine aliquots will be frozen at -80°C and stored for subsequent measurements. Peripheral blood mononuclear cells (PBMCs) may be isolated from blood for analysis. We are already storing buffy coat and extracting DNA in the first phase of this study. While we do not expect the DNA to change between visits, we will store additional buffy coat samples to allow for back-up samples for DNA extraction in the event of any sample failures from phase 1, or for any follow-up analyses. Samples will be prepared for metabolite measurement by methanol extraction and centrifugation in [name] laboratory using standard protocols³¹. 2-AAA and other metabolites and biomarkers (e.g. lysine, creatinine, insulin) will be measured at Vanderbilt core facilities (e.g. Mass Spectrometry core, Hormone Assay core). DNA from buffy coat will be extracted and submitted for genotyping at the Vanderbilt Technologies for Advanced Genomics (VANTAGE) core. Microbial DNA will be extracted from stool, prepared for sequencing (16S V4 or metagenomic), and sequenced at VANTAGE. For possible future

investigations, excess blood, urine and stool samples will be frozen and stored in [name] laboratory.

Genomic Data: Genomic data will be deposited in dbGap, a controlled-access database, and will be made available as part of the Policy for Sharing of Data Obtained in NIH Supported or Conducted Genomic Studies. All deposited data and metadata will be documented, per NIH guidelines. All data will be de-identified to protect study participants' identities.

